## 1. INTRODUCTION AND RATIONALE

Sickle cell disease (SCD) is a common hemoglobinopathy caused by a single point mutation in the 6th position of the  $\beta$ -globin gene (substitution of valine for glutamic acid), which leads to the replacement of normal hemoglobin (HbA) by sickle-hemoglobin (HbS). SCD is a heterogeneous disorder, with clinical manifestations including chronic hemolytic anaemia, increased susceptibility to infections due to functional asplenicism, recurrent painful vaso-occlusive episodes and chronic ischemic organ damage resulting in a diminished quality of life and early death. (1)

One of the most severe complications during vaso-occlusive painful crisis is the acute chest syndrome (ACS), occurring in 30% of all sickle cell patients at least once in their life. (2) ACS is a major cause of death in sickle cell patients and frequently develops during and shortly after the start of a painful crisis. (3) The mortality of this complication is around 4,3% and is the most frequent cause of intensive care unit (ICU) admission for sickle cell patients. ACS is defined as the presence of a new pulmonary infiltrate (on chest X-ray) in combination with clinical symptoms such as fever or respiratory symptoms in a patient with SCD. (2) Though the exact cause is unknown, several factors, such as pulmonary fat embolism, bacterial or viral infection, thromboembolic occlusion and hypoventilation due to thoracic bone infarction, have been associated with ACS.(4) Nowadays, treatment focuses primarily on antibiotic therapy and (exchange) blood transfusion. (5)

Incentive spirometry has been demonstrated to be effective as primary prevention of the development of ACS in children admitted with a vaso-occlusive painful crisis. (6) However, the effect of incentive spirometry in prevention of ACS in adult sickle cell patients during painful crisis has not been studied so far. Therefore, the aim of our study is to evaluate the efficacy of incentive spirometry on the incidence of ACS in adult sickle cell patients admitted with a vaso-occlusive painful crisis.

Since phospholipase A2 (sPLA2), an inflammatory mediator, can predict ACS and has been used successfully as a screening tool for early intervention, (7) plasma levels of sPLA2 will also be assessed in this study in order to related the efficacy of spirometry to this biomarker. Furthermore, serum levels of procalcitonin, which is a strong indicator of bacterial infection,(8) will be assessed at presentation in order to recognize a subgroup of infection related ACS and to assess the efficacy of spirometry in this subpopulation. In addition, PCR's on respiratory viruses (*respiratory syncytial virus, human metapneumovirus, influenza A and B, parainfluenza 1-4, adenovirus, coronavirus, parechovirus, rhinovirus* and *bocavirus*) and atypical bacteria such as *C. pneumoniae, C. psittaci,* and *M. pneumoniae* will performed on throat swaps taken at randomization. *L. pneumophila* antigen will be analyzed in a urine sample.

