## **3. STUDY OBJECTIVES**

1. To evaluate the efficacy of incentive spirometry in primary prevention of ACS in adult sickle cell patients during painful crisis.
2. To relate the efficacy of incentive spirometry to plasma levels of sPLA2 and serum levels of procalcitonin.
3. To evaluate whether plasma sPLA2 levels may be helpful to stratify patients in high and low risk groups and to evaluate the value of incentive spirometry in these groups to prevent ACS.
4. To evaluate whether serum procalcitonin may stratify patients with an ACS related to an infectious and non-infectious pathogenesis and to evaluate the value of incentive spirometry to prevent ACS.
5. To identify the micro bacterial organisms responsible for the development of an acute chest syndrome and to relate this with the procalcitonin plasma levels.

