## **4. STUDY DESIGN**

A multicentre randomized controlled clinical trial, studying the effect of incentive spirometry on the incidence of ACS in comparison with standard care in adult sickle cell patients admitted with a vaso-occlusive painful crisis. Endpoint of the study is the development of an ACS.

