## **5.3. Exclusion criteria**

1. Blood transfusion in the preceding three months
2. Diagnosis of ACS at presentation
3. Age < 18 years

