### **6.3. Blood samples and laboratory analysis**

#### **6.3.1. Blood**

Blood will be drawn at randomization:

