## **7. STATISTICS**

The non-parametric Mann-Whitney U (or when necessary Kruskal-Wallis) test will be applied for between group comparisons. Spearman rank correlation analysis will be used to study the relationship between different laboratory results. Two-tailed p values  $\leq 0.05$  are considered statistically significant. We are planning a study of independent cases and controls with 1 control(s) per case. Prior data indicate that the failure rate among controls is 0,5. Failure is defined as the development of an Acute Chest Syndrome as defined in the protocol at page 3, line 11. If the true relative risk of failure for experimental subjects relative to controls is 0,3. We will need to study 32 experimental subjects and 32 control subjects to be able to reject the null hypothesis that this relative risk equals 1 with

probability (power) 0,8. To correct for dropouts the study population will set at 35 subjects per treatment arm. The Type I error probability associated with this test of this null hypothesis is 0,05. We will use a chi-squared statistic to evaluate this null hypothesis. The sample size was calculated using Stata/SE, version 10.1 (sampsi program, StataCorp LP, Texas, USA).

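### Spirometry efficacy is to be assessed in a subgroup defined by having the endpoint (infection-related ACS), where prevention of ACS cannot be estimated

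*Protocol*

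**What the plan says.** Section 1 (Introduction and Rationale) states that serum procalcitonin "will be assessed at presentation" and gives the purpose: "in order to recognize a subgroup of infection related ACS and to assess the efficacy of spirometry in this subpopulation".

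Section 3, objective 4, has two clauses. The first is "To evaluate whether serum procalcitonin may stratify patients with an ACS related to an infectious and non-infectious pathogenesis". The second asks about the value of spirometry in preventing ACS and does not say in whom.

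Three other places fix the context:

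- Section 4: "Endpoint of the study is the development of an ACS".
- Section 5.3 lists as an exclusion "Diagnosis of ACS at presentation".
- Section 6.3.1: "Blood will be drawn at randomization". The serum tube for procalcitonin is part of that draw.

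**The concern.** A preventive effect compares the risk of the event between arms among people who could still have it or escape it. A subgroup of patients with infection-related ACS contains only people who had the event. Prevention has no meaning inside it.

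Something else could still be compared between arms within the cases, such as the share that looks infectious. But randomisation does not protect that comparison. If spirometry works, it changes who becomes a case, so the spirometry cases and the control cases are differently selected groups. A difference between them could be reported as spirometry failing in, or even promoting, infectious ACS when it had reduced it.

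**Working it through.** **Step 1: the plan's own figure.** Section 7 gives a control failure rate of 0.5, a relative risk of 0.3 (hence 0.5 × 0.3 = 0.15 on spirometry), two-sided alpha 0.05, power 0.8 and 1:1 allocation. With mean rate 0.325:

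- Uncorrected n = [1.960 × √(2 × 0.325 × 0.675) + 0.842 × √(0.5 × 0.5 + 0.15 × 0.85)]² / 0.35² = 26.9.
- With continuity correction, n′ = (n/4) × [1 + √(1 + 4/(n × 0.35))]² = 32.4.

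The stated 32 per arm is reproduced (33 if rounded up). The planning rates can therefore be used as they stand, and the sample size is not in question.

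**Step 2: who is in the subgroup.** ACS at presentation is an exclusion, so no eligible patient has ACS at entry. Every ACS in the trial therefore arises after entry and is an endpoint event. A patient with infection-related ACS is by definition one with the endpoint.

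**Step 3: what can be estimated there.** P(ACS | ACS) = 1 in each arm, so the relative risk is 1/1 = 1 for any true effect, including the planned 0.3.

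**Step 4: size of the case set.** With 35 per arm: 35 × 0.5 = 17.5 control cases and 35 × 0.15 = 5.25 spirometry cases, 22.75 in all. With 32 per arm: 16 + 4.8 = 20.8. The infection-related subgroup is some part of these. The Protocol does not give the fraction.

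**Step 5: what a within-case comparison can do.** Suppose, as an illustration not taken from the Protocol, that 30% of control cases are infectious and that spirometry has a relative risk of 0.6 for infectious ACS. To keep the overall relative risk at 0.3, the non-infectious relative risk must be (0.30 − 0.3 × 0.6)/0.7 = 0.17.

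| Quantity | Control | Spirometry | Ratio |
|---|---|---|---|
| Infectious ACS, all randomised | 0.5 × 0.3 = 0.15 | 0.15 × 0.6 = 0.09 | 0.6 |
| Non-infectious ACS, all randomised | 0.5 × 0.7 = 0.35 | 0.15 − 0.09 = 0.06 | 0.17 |
| Infectious share among ACS cases | 0.15/0.50 = 30% | 0.09/0.15 = 60% | 2.0 |

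The infectious share doubles on spirometry although infectious ACS fell by 40%. If the relative risk is instead 0.3 for both causes, the share is 30% in both arms and a real 70% reduction is invisible. With all randomised patients as denominator, the correct effects are recovered in both cases.

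**Step 6: precision of the valid alternative.** The marker split is not given, so a 50/50 split is assumed, with 16 to 17 patients per arm in each half. Uncorrected power for 0.5 against 0.15 within one half is 57% to 59%. For a difference in effect between halves of relative risk 0.3 against 1.0 (control rate 0.5 in both), the variance of each log relative risk is (1 − p₁)/(n p₁) + (1 − p₂)/(n p₂). With n = 17 the two variances are 0.392 and 0.118, the standard error is √0.510 = 0.714, and z = 1.204/0.714 = 1.69. Power is about 39% (37% with n = 16).

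**The case against.** The strongest reply is that this is loose wording. Procalcitonin is taken at presentation, when nobody eligible has ACS, so the authors may mean patients whose baseline procalcitonin suggests infection. That is a legitimate baseline subgroup. Section 7 also prescribes no test confined to ACS cases. This is a fair guess at the intent, and it is why the repair is easy. But the text names the subgroup as ACS and then places the efficacy assessment inside it. An analyst following it would condition on the endpoint.

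Three stronger readings are tempting, and the Protocol does not support them.

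- *Objective 4 cannot be answered at all.* Its first clause is a classification question that is properly asked among cases. Its second clause is not restricted to cases, whereas objective 3 does tie spirometry's value to its groups. Objective 4 is ambiguous and only partly affected.
- *The listed tests cannot relate efficacy to sPLA2 or procalcitonin.* Section 7 names no test of whether the effect differs by marker level, and its Spearman analysis is confined to laboratory results ("Spearman rank correlation analysis will be used to study the relationship between different laboratory results"). But the chi-squared test can be run within strata of the baseline marker, which serves objective 3 ("may be helpful to stratify patients in high and low risk groups"). An interaction model and a cut-off are details that a statistical analysis plan, not shown here, may supply. Their absence is not an error in this Protocol.
- *Misleading subgroup p-values or a data-driven cut-off are planned.* No section says so. Power figures for such analyses, including those in step 6, rest on splits and effects that the Protocol does not give.

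**Conclusion.** The concern holds for the Introduction's procalcitonin sentence and, by ambiguity, for the second clause of objective 4. As written, efficacy is to be assessed among patients who all have the endpoint. Prevention cannot be estimated there, and any other comparison of arms among the roughly 23 expected cases is open to selection by treatment. That count rests on the Protocol's own rates and on 35 analysed patients per arm. The 30% against 60% example rests on assumed cause-specific effects and shows the direction of possible error, not its likely size.

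The primary hypothesis, its chi-squared test and the sample size are untouched. This is a secondary objective and severity is minor to moderate.

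**What to change.** Reword the procalcitonin sentence in section 1 and the second clause of objective 4 in one or both of these ways:

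1. Assess the effect of spirometry on ACS in all randomised patients, according to the procalcitonin value drawn at randomisation.
2. Analyse infection-related ACS and non-infection-related ACS as two separate outcomes, each with all randomised patients in each arm as denominator, and with the cause classified in the same way in both arms.

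Leave the first clause of objective 4 as a classification question among cases. Label the efficacy analyses exploratory and report estimates with confidence intervals. An arm-by-marker interaction estimate with its interval would be a sensible way to address objective 2, but that is a suggestion and not a correction.

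The cost is a few sentences and a small amount of analysis. The serum is already to be drawn at randomisation and stored, so no new data are needed. The downside is imprecision: with 70 patients the subgroup and interaction estimates will be wide, and the report should say so.

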## **2. HYPOTHESES**

We hypothesize that incentive spirometry will reduce the incidence of ACS in adult sickle cell patients admitted with an acute vaso-occlusive painful crisis.

## **3. STUDY OBJECTIVES**

1. To evaluate the efficacy of incentive spirometry in primary prevention of ACS in adult sickle cell patients during painful crisis.
2. To relate the efficacy of incentive spirometry to plasma levels of sPLA2 and serum levels of procalcitonin.
3. To evaluate whether plasma sPLA2 levels may be helpful to stratify patients in high and low risk groups and to evaluate the value of incentive spirometry in these groups to prevent ACS.
4. To evaluate whether serum procalcitonin may stratify patients with an ACS related to an infectious and non-infectious pathogenesis and to evaluate the value of incentive spirometry to prevent ACS.
5. To identify the micro bacterial organisms responsible for the development of an acute chest syndrome and to relate this with the procalcitonin plasma levels.

## **4. STUDY DESIGN**

A multicentre randomized controlled clinical trial, studying the effect of incentive spirometry on the incidence of ACS in comparison with standard care in adult sickle cell patients admitted with a vaso-occlusive painful crisis. Endpoint of the study is the development of an ACS.

## **5. STUDY POPULATION**

### **5.1. Patients**

Adult ( $\geq 18$  years) sickle cell patients (HbSS, HbSC, HbS $\beta^0$ - or HbS $\beta^+$ -thalassemia) presenting with an acute painful crisis and thoracic pain without signs of an ACS will be asked to participate in this study. After informed consent is obtained, patients will be randomized for incentive spirometry (study group) or standard care (control group).

## **5.2. Inclusion criteria**

1. High performance liquid chromatography confirmed diagnosis of HbSS, HbSC, HbS $\beta^0$ - or HbS $\beta^+$ -thalassemia genotypes.
2. Written informed consent by the patient.
3. Thoracic or back pain above the diaphragm.
4. Hospital admission due to vaso-occlusive painful crisis.

## **5.3. Exclusion criteria**

1. Blood transfusion in the preceding three months
2. Diagnosis of ACS at presentation
3. Age < 18 years

## **6. STUDY PROCEDURES**

### ***6.1. Study group***

Upon inclusion in the study, blood samples will be drawn via venipuncture and urine sampling will be performed according to the protocol. Chest X-ray of each patient will be taken at the emergency department (ED) and repeated on day 5 of hospital admission or sooner if clinically indicated.

Patients in the study group will be educated in the use of the spirometer (RespifloTMMFS, Kendall) and the study protocol by the investigator. During admission patients have to inhale 10 times through the spirometer every 2 hours (between 8 a.m. and 10 p.m.) until at least 24 hours after the pain has subsided. If awake, patients may use the spirometry also between 10 p.m. and 8 a.m. Patients are asked to register every time they inhale through the spirometer and pain scores will be assessed (Visual Analog Scores).

Attending nurses under supervision of a specialized sickle cell nurse on the ward, together with the patient, will evaluate the spirometry protocol and pain scores daily. Patients will continue to receive the standard care as well (see below).

### ***6.2. Control group (standard care only)***

Patients in the standard care group will be evaluated equally but will receive standard care consisting of pain medication (iv/sc morphine), hydration and antibiotics in case of fever (>38.5 Celsius) according to local protocol. Oxygen therapy should be considered in case of hypoxia (blood oxygen saturation  $\leq 92$  %, measured with finger pulse oximeter).

### **6.3. Blood samples and laboratory analysis**

#### **6.3.1. Blood**

Blood will be drawn at randomization:

##### ***EDTA blood (2x 4 cc)***

- Hemoglobin levels, red blood cell counts, reticulocyte counts, leukocyte counts and differentiation, platelet counts will be determined with an automated cell counter.

##### ***Heparin gel tube (1x 4.5 cc)***

- Creatinin, ASAT, ALAT, AF, gGT, LDH, indirect bilirubin and proBNP levels will be determined according to local protocols.

##### ***Serum (1x 10 cc)***

- Serum samples will be stored at -70°C for future analysis of high sensitive C-reactive protein (CRP), soluble vascular cell adhesion molecule 1 (sVCAM-1) and procalcitonin which will be determined with ELISA methods.

##### ***Citrated plasma (1x 4,5 cc)***

- Citrated plasma samples will be stored at -70°C until analysis of sPLA2, pro-thrombin fragments (F1+2), D-dimer levels, protein S (free and total) and C activity and von Willebrand activity (vWF-Act)

#### **6.3.2. Bacterial and viral analysis**

- Throat swabs for bacterial and viral pathogens will be taken at randomization and analyzed by PCR for respiratory viruses (*respiratory syncytial virus, human metapneumovirus, influenza A and B, parainfluenza 1-4, adenovirus, coronavirus, parechovirus, rhinovirus and bocavirus*) and atypical bacteria (*C. pneumoniae, C. psittaci, and M. pneumonia*).

## **7. STATISTICS**

The non-parametric Mann-Whitney U (or when necessary Kruskal-Wallis) test will be applied for between group comparisons. Spearman rank correlation analysis will be used to study the relationship between different laboratory results. Two-tailed p values  $\leq 0.05$  are considered statistically significant. We are planning a study of independent cases and controls with 1 control(s) per case. Prior data indicate that the failure rate among controls is 0,5. Failure is defined as the development of an Acute Chest Syndrome as defined in the protocol at page 3, line 11. If the true relative risk of failure for experimental subjects relative to controls is 0,3. We will need to study 32 experimental subjects and 32 control subjects to be able to reject the null hypothesis that this relative risk equals 1 with

probability (power) 0,8. To correct for dropouts the study population will set at 35 subjects per treatment arm. The Type I error probability associated with this test of this null hypothesis is 0,05. We will use a chi-squared statistic to evaluate this null hypothesis. The sample size was calculated using Stata/SE, version 10.1 (sampsi program, StataCorp LP, Texas, USA).

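### The primary chi-squared test is valid but ignores genotype, which is confirmed in every patient at entry; a test stratified by genotype class would be a cheap improvement

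*Protocol*

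**What the plan says.** Protocol section 7 names the test for the endpoint: "We will use a chi-squared statistic to evaluate this null hypothesis". It names no stratification factor or covariate. The design values beside it are a control risk of 0.5 ("Prior data indicate that the failure rate among controls is 0,5"), a relative risk of 0.3, "probability (power) 0,8" and a two-sided level of 5% ("The Type I error probability associated with this test of this null hypothesis is 0,05"; "Two-tailed p values" elsewhere in the section). They lead to 32 patients per arm, raised to 35 for dropout.

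Section 5.2 admits four genotypes and makes laboratory confirmation an entry condition: "High performance liquid chromatography confirmed diagnosis of HbSS, HbSC" and the two HbS-beta-thalassaemia forms. Section 4 describes "A multicentre randomized controlled clinical trial, studying the effect of incentive spirometry on the incidence of ACS". Section 1 remarks that "SCD is a heterogeneous disorder". Section 5.1 says that patients are randomised after consent. The protocol text available for review mentions no stratification of that randomisation, either for or against. It also gives no number of recruiting centres, no expected genotype mix, and no ACS risk by genotype or centre.

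**The concern.** The trial rests on one comparison of two proportions in at most 70 patients. Genotype is on file for everyone before randomisation. If it predicts ACS, a chance difference in genotype mix shifts the crude comparison, and the planned test cannot answer the objection that one arm simply had milder disease. An adjustment chosen after the imbalance has been seen convinces far less than one fixed beforehand. At stake is mainly the credibility of the result and, to a smaller and uncertain degree, its power.

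**Working it through.** **1. The plan's own figure.** With p1 = 0.50, p2 = 0.3 × 0.50 = 0.15, d = 0.35, mean p = 0.325, two-sided alpha 0.05 and power 0.80:

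n = [1.96·√(2 × 0.325 × 0.675) + 0.842·√(0.25 + 0.1275)]² / 0.35² = (1.298 + 0.517)² / 0.1225 ≈ 26.9.

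With continuity correction, n' = (n/4)·[1 + √(1 + 4/(n·d))]² = (26.9/4)·[1 + √1.425]² ≈ 32.4. The stated 32 per arm therefore reproduces to within one patient and rests on the crude two-proportion comparison. By formula, the uncorrected chi-squared has 86.6% power at 32 per arm and 89.6% at 35.

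**2. How often the arms differ in genotype mix.** Assume 60% of patients in the more severe class (HbSS/HbS-beta0) and simple randomisation. The counts are then two independent Binomial(35, 0.6) variables. The probability that the shares differ by at least 15 points in either direction (six patients or more, since 5/35 is 14.3 points) is 17.9%. It runs from 18.8% for a 50% share to 12.8% for a 75% share.

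With class risks of 70% and 20%, a 15-point gap moves the expected crude risk difference by 0.15 × (0.70 − 0.20) = 7.5 points, against a planned effect of 35 points.

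**3. What such a gap does to the test.** These are simulations with no treatment effect, restricted to trials in which the spirometry arm has at least 15 points fewer severe genotypes. The crude test falsely favours spirometry in 5.4% (class risks 60%/35%), 7.4% (65%/27.5%) or 9.8% (70%/20%) of them, where 2.5% is nominal. CMH by genotype class stays below 3%. Averaged over all randomisations the crude test does not have this problem.

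**4. Power with genotype class as the only stratum.** The statistic is X² = [Σ(aᵢ − n₁ᵢmᵢ/Nᵢ)]² / Σ[n₁ᵢn₀ᵢmᵢ(Nᵢ − mᵢ)/(Nᵢ²(Nᵢ − 1))], where in stratum i aᵢ is ACS cases on spirometry, n₁ᵢ and n₀ᵢ the arm sizes, mᵢ all ACS cases and Nᵢ all patients. Simulated with 35 per arm, a 60/40 split, simple randomisation and relative risk 0.3. Each pair of control risks averages to 0.50, for example 0.6 × 0.65 + 0.4 × 0.275 = 0.50.

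| Assumed control risks, severe/mild | Crude | CMH by genotype class |
|---|---|---|
| 50%/50% (not prognostic) | 0.903 | 0.896 |
| 55%/42.5% | 0.903 | 0.899 |
| 60%/35% | 0.903 | 0.906 |
| 65%/27.5% | 0.903 | 0.917 |
| 70%/20% | 0.902 | 0.933 |

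The change runs from −0.7 to +3.1 points. Simulated type I error is 0.047 to 0.053 for CMH. For the uncorrected crude test it is about 0.043 at 35 per arm and about 0.06 at 32 per arm.

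**5. Adding centre.** Simulated power (%), crude → CMH, at 32 per arm with an assumed 67/33 split, equal centres without a centre effect, and simple randomisation:

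| Control risks | Genotype only | Genotype × 3 centres | Genotype × 5 centres |
|---|---|---|---|
| 0.50/0.50 | 87.5 → 86.6 | 87.7 → 84.5 | 87.5 → 81.4 |
| 0.55/0.40 | 87.1 → 86.8 | 87.8 → 85.2 | 87.6 → 82.5 |
| 0.60/0.30 | 87.6 → 88.2 | 87.5 → 86.3 | 87.5 → 83.8 |
| 0.70/0.10 | 87.6 → 92.1 | 87.4 → 90.8 | 87.4 → 89.2 |

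Joint strata lose power in every row but the last, by up to 6.1 points. The reason is sparseness: with five centres, a mild-class stratum holds about 64 × 0.33 / 5 ≈ 4 patients, about two per arm, and some have only one arm. If randomisation is itself stratified by the same factors, the change is only about −1 to +3 points.

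**The case against.** The best defence of the plan is that nothing in section 7 is wrong. A chi-squared test is valid for a binary endpoint in a randomised trial, its type I error already allows for chance imbalance, and it matches the sample-size calculation beside it. An adjusted analysis could also sit in a statistical analysis plan that is not shown. All of this stands, and it limits the point to an improvement.

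Four stronger readings are tempting, and the documents do not support them.

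- **A test stratified by genotype and centre gains power.** It often loses power at this size, and the number and size of centres are not given.
- **Imbalance is likely.** About 18% is not likely; more than four trials in five would show no gap of that size.
- **Randomisation is unstratified.** The text is silent on this. If randomisation was stratified by genotype, step 2 does not apply.
- **The power gain is large.** A rise from 0.77 to 0.86 can be produced, but only with a sixfold risk ratio between classes (75% against 12.5%) and a relative risk of 0.4 in place of the protocol's 0.3.

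The remark on heterogeneity in section 1 introduces the range of clinical manifestations. It does not say that genotype predicts ACS among patients admitted with thoracic or upper back pain.

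What remains is that the protocol itself chose the test, that the stratifier is recorded for everyone, and that fixing its use in advance costs almost nothing.

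**Conclusion.** The point holds as a cheap improvement limited to genotype class. The crude test is valid; it leaves a known baseline factor unused. The main benefit is a prespecified answer to a genotype imbalance of 15 points or more, which would arise in about 18% of trials (13% to 19% for severe shares from 75% down to 50%) under simple randomisation. With the planned relative risk, power changes by about −1 to +3 points over assumed class risks from 50%/50% to 70%/20%, with type I error near 5%.

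The genotype split, the class risks and the centre numbers are all assumptions. So is the grouping of HbSS with HbS-beta0 against HbSC with HbS-beta+, because the protocol does not rank the genotypes. A reader should not infer that the planned analysis is in error or that power will certainly rise.

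**What to change.** In section 7, before any outcome data are seen by arm, make the primary test a CMH chi-squared stratified by genotype class (HbSS/HbS-beta0 against HbSC/HbS-beta+). Report the Mantel-Haenszel risk ratio and risk difference with 95% CI, and keep the crude chi-squared as a sensitivity analysis. Add centre as a stratum only if randomisation was stratified by it or the centres are few and large. If the statistical analysis plan already contains an adjusted analysis, bring the two documents into line.

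The cost is a sentence or two, with no new data and no change to the sample size. The price is about 1 point of power at worst, if genotype turns out not to be prognostic.
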